6.3.2 Study follow-up

Both as-treated (AT) and intention-to-treat (ITT) analyses will be conducted with treatment defined as the index drug on the day of cohort entry. Because adherence in the real world databases is expected to be much worse than in the trial, the AT analysis is the **primary** analysis, as it targets the relative hazard of outcomes on treatment.

For the AT analyses, the follow-up will start the day after initiation of linagliptin and comparator and will continue until the earliest date of the following events:

- The first occurrence of the outcome of interest, unless otherwise specified for selected outcomes,
- The date of end of continuous registration in the database,
- End of the study period,
- Measured death event occurs,
- Nursing home admission

- Nursing home admissions are considered a censoring event because the data sources utilized typically provide little to no data on a patient, particularly on drug utilization, after admission. We will utilize this as an exclusion reason for cohorts for the same reason.
- The date of drug discontinuation, defined as the date of the last continuous treatment episode of the index drug (linagliptin and comparator) plus a defined grace period (i.e., 30 days after the end of the last prescription's days' supply in main analyses).
- The date of augmentation or switching from an exposure to a comparator or any other agent in the comparator class and vice versa (e.g. switching from glimepiride to glipizide would be a censoring event);
 - A dosage change on the index treatment does not fulfill this criterion
 - An added treatment that is not part of the exposure or comparator group does not fulfill this criterion (e.g. if a linagliptin user adds insulin, he or she does not get censored at the time of insulin augmentation)

For the ITT analyses, the censoring based on the augmentation/switching and treatment discontinuation will be replaced with a maximum allowed follow-up time of 365 days.

7. Initial Feasibility Analysis

Action report links:

Optum: <https://bwh-dope.aetion.com/#/projects/details/702/results/30636/result/0>

Marketscan: <https://bwh-dope.aetion.com/#/projects/details/701/results/30634/result/0>

Medicare: <https://bwh-dope.aetion.com/#/projects/details/703/results/30635/result/0>

Date conducted: rerun on January 28, 2019

Complete Aetion feasibility analysis using age, sex, and CCI as the only covariates and the primary endpoint (Section 6.3.1) as the outcome. No measures of association will be computed nor will incidence rates stratified by treatment group.

- Report patient characteristics by treatment group
- Report summary parameters of the overall study population
- Report median follow-up time by treatment group
- Report reasons for censoring in the overall study population

8. Initial Power Assessment

Action report links:

Optum: <https://bwh-dope.aetion.com/#/projects/details/702/results/30639/result/1>

Marketscan: <https://bwh-dope.aetion.com/#/projects/details/701/results/30637/result/1>

Medicare: <https://bwh-dope.aetion.com/#/projects/details/703/results/30638/result/1>

Date conducted: rerun on January 28, 2019

In order to complete the initial power analysis, the dummy outcome of a 90-day gap in database enrollment will be used. This outcome is used to ensure that no information on the comparative risks of the outcomes of interest are available at this stage. Complete a 1:1 PS-matched comparative analysis using this outcome. PS should include only 3 covariates: age, sex, and combined comorbidity index. Power calculations are based on the formulas from Chow et al. (2008).

- Stop analyses until feasibility and power are reviewed by primary investigators and FDA. Reviewers evaluate the results of the analyses described above in Sections 7 and 8, including numbers of patients, patient characteristics, follow-up time, and reasons for censoring by treatment group, as well as overall rates of outcomes and study power. These parameters are re-evaluated and reported in the subsequent sections, after incorporating feedback and refining the protocol.

Reviewed by PI:	[name]	Date reviewed:	10/26/18
Reviewed by FDA:	[name]	Date reviewed:	12/19/18
Reasons for stopping analysis (if required):			

9. Balance Assessment after PS matching

Action report name:

Optum: <https://bwh-dope.aetion.com/projects/details/702/results/44872/result/0>

Marketscan: <https://bwh-dope.aetion.com/projects/details/701/results/44873/result/0>

Medicare: <https://bwh-dope.aetion.com/projects/details/703/results/45415/result/0>

Date conducted: 11/18/2019 (Medicare 11/30/2019)

After review of initial feasibility and power analyses, complete creation of the remaining covariates (see Table 1 below for list of covariates). Again, using the dummy outcome of a 90-day gap in database enrollment, complete a 1:1 PS-matched analysis. The PS should include the complete list of covariates (excluding laboratory values, which are missing in some patients).

- Provide plot of PS distributions stratified by treatment group.

Note- Please refer to **Appendix B**.

- Report covariate balance after matching.

Note- For Table 1, please refer to **Appendix B**.

- Report reasons for censoring by treatment group.

	Overall	Referent	Exposure
Dummy Outcome	0 (0.00%)	0 (0.00%)	0 (0.00%)
Death	1,704 (1.67%)	929 (1.82%)	775 (1.52%)
Start of an additional exposure	4,752 (4.67%)	746 (1.47%)	4,006 (7.87%)
End of index exposure	58,792 (57.74%)	29,602 (58.14%)	29,190 (57.33%)
Specified date reached	18,168 (17.84%)	9,825 (19.30%)	8,343 (16.39%)
End of patient enrollment	9,190 (9.02%)	4,583 (9.00%)	4,607 (9.05%)
Switch to other SUs (for censoring) + nursing home admission	9,224 (9.06%)	5,230 (10.27%)	3,994 (7.84%)

- Report follow-up time by treatment group.

Patient Group	Median Follow-Up Time (Days) [IQR]		
	Optum	MarketScan	Medicare
Overall Patient Population	118 [58-286]	128 [63-304]	137 [65-323]
Referent	122 [65-304]	148 [86-344]	148 [86-344]
Exposure	118 [58-269]	127 [58-303]	127 [58-303]

- Report overall risk of the primary outcome.

	Optum	Marketscan	Medicare
Risk per 1,000 patients	16.55	18.7	42.47

10. Final Power Assessment

Date conducted: 12/01/2019

- Re-calculate power in the appropriate excel table, using the revised number of matched patients from the PS-match in Section 9. All other parameters in the table should be the same as in Section 8. If the study is to be implemented in more than one database, copy and paste excel sheet to report power for each database separately and for the pooled analysis that uses data from all databases together. Power calculations are based on the formulas from Chow et al. (2008).

- Pooled

Non-inferiority Analysis	
Number of patients matched	
Reference	50,915
Exposed	50,915
Risk per 1,000 patients	25.91
Assumed HR from RCT	1
Alpha (2-sided)	0.05
Non-inferiority margin	1.3
Number of events expected	2638.4153
Power	0.999999116

- Optum

Non-inferiority Analysis	
Number of patients matched	
Reference	8,880
Exposed	8,880
Risk per 1,000 patients	16.55
Assumed HR from RCT	1
Alpha (2-sided)	0.05
Non-inferiority margin	1.3
Number of events expected	293.928
Power	0.613734405

- Marketscan

Non-inferiority Analysis	
Number of patients matched	
Reference	8,716
Exposed	8,716
Risk per 1,000 patients	18.7
Assumed HR from RCT	1
Alpha (2-sided)	0.05
Non-inferiority margin	1.3
Number of events expected	325.9784
Power	0.658551313

- Medicare

Non-inferiority Analysis	
Number of patients matched	
Reference	33,319
Exposed	33,319
Risk per 1,000 patients	42.47
Assumed HR from RCT	1
Alpha (2-sided)	0.05
Non-inferiority margin	1.3
Number of events expected	2830.11586
Power	0.99999974

- Stop analyses until balance and final power assessment are reviewed by primary investigators, FDA, and assigned members of advisory board. Reviewers evaluate the results of the analyses described above in Sections 9 and 10, including numbers of patients, balance in patient characteristics, follow-up time, and reasons for censoring by treatment group, as well as overall rates of outcomes and study power.

Reviewed by PI:	[name]	Date reviewed:	12/9/19
Reviewed by FDA:	[name]	Date reviewed:	12/20/19
Reasons for stopping analysis (if required):			

11. Study Confidence and Concerns

Deadline for voting on study confidence and listing concerns: 12/20/19

- If final feasibility and power analyses are reviewed and approved, proceed to the remaining protocol steps.
- All study team and advisory board members that review this protocol should at this stage provide their level of confidence for the success of the RWD study in the [Google Form](#). This form also provides space for reviewers to list any concerns that they feel may

contribute to a failure to replicate the findings of the RCT, including differences in study populations, poor measurement of study variables, or residual confounding. All responses will be kept confidential and individual-level results will only be shared with the individual respondent.

12. Register study protocol on clinicalTrials.gov

Date conducted:

- Register the study on [clinicalTrials.gov](https://clinicaltrials.gov) and upload this document.

13. Comparative Analyses

Action report name:

Date conducted:

13.1 For primary analysis:

- In the PS-matched cohort from Section 9, calculate the HR for each outcome for linagliptin versus referent patients using a Cox proportional hazards model.

13.2 For secondary analyses:

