5.1 Cohort Summary

This study will involve a new user, parallel group, cohort study design comparing linagliptin to the 2nd generation sulfonylurea (SU) antidiabetic class as a proxy for placebo. 2nd generation SUs are not known to have an impact on the outcome of interest. In addition, SUs were the most frequent background treatment in CARMELINA (after metformin), and DPP4i and SUs are preferentially prescribed to similarly older patients in real world (Paterno et al., 2019). The patients will be required to have continuous enrollment during the baseline period of 180 days before initiation of linagliptin or a comparator drug (cohort entry date). Follow-up for the outcome (3P-MACE), begins the day after drug initiation. As in the trial, patients are allowed to take other antidiabetic medications during study follow-up.

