Excluded based on Exclusion 11 part 1- life expectancy less than 5 years [using combined comorbidity index as a proxy (365 days)]	-2,263	129,818	-1,125	129,334	-12,200	422,949
Excluded based on Exclusion 11 part 2- History of Malignant Neoplasm (within last 3 years)	-4,153	125,665	-4,128	125,206	-14,241	408,708
Excluded based on Exclusion 12- ACS/unstable angina (≤ 2 months prior)	-374	125,291	-332	124,874	-788	407,920
Excluded based on Exclusion 13- Stroke or TIA (≤ 3 months prior)	-2,292	122,999	-1,981	122,893	-7,081	400,839
Final cohort		122,999		122,893		400,839

* Medicare database includes only patients ≥ 65 years of age with at least one diagnosis for diabetes, heart failure, or stroke.

** Exclusion 8 and Exclusion 10 collapsed for adherence to CMS suppression guidelines.

6. Variables

6.1 Exposure-related variables:

Study drug:

The study exposure of interest is initiation of linagliptin. Initiation will be defined by no use of linagliptin or a comparator in the prior 6 months before treatment initiation (washout period).

Comparator agents:

- Initiators of linagliptin will be compared to initiators of-
 - 2nd generation sulfonylureas

Because linagliptin and comparators are frequently used as second or third line treatments of T2DM, we expect it to be unlikely that linagliptin and comparators are initiated in patients with substantially different baseline risk for proposed outcomes.

6.2 Preliminary covariates:

- Age
- Sex
- Combined Comorbidity Index (CCI), measured over the baseline covariate assessment period, defined as 180 days prior to and including index date

Covariates listed above represent only a small subset of covariates that will ultimately be controlled for in the design and analysis. We use the covariates above only for initial feasibility analyses to judge whether there is likely to be sufficient overlap between treatment groups to proceed with the study. Remaining covariates are defined only after the study has passed the initial feasibility analysis and the initial power assessment and are listed in Table 1 (**Appendix B**). These covariates are based on those used by Patorno et al. (2019).

6.3 Outcome variables and study follow-up:

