
II. Evidence of impaired renal function with predefined UACR, with or without CV co-morbidities, defined as follows (and/or criteria):
 
 - Impaired renal function (as defined by MDRD formula) with an eGFR: 15-<45 mL/min/1.73 m² at visit 1 (screening) with any UACR. - Impaired renal function (as defined by MDRD formula) with an eGFR ≥ 45-75 mL/min/1.73 m² at visit 1 (screening) with an UACR > 200 mg/g creatinine or 
> 200 μg/min (microgram albumin per minute) or > 200 mg/24 h [milligram albumin per 24 hours] demonstrated in two out of three unrelated spot urine or timed samples in the last 24 months prior to randomization.
	
Measured 180 days prior to drug initiation in any diagnosis position in inpatient or outpatient filters:
 
CKD stage 3 and stage 4
 
585.3x-585.4x
	
CKD stage 1: GFR > 90 CKD stage 2: GFR 60 to 89 CKD stage 3a: GFR 45 to 59 CKD stage 3b: GFR 30 to 44 CKD stage 4: GFR 15 to 29 CKD stage 5: GFR < 15

EXCLUSION CRITERIA		

1) Type 1 diabetes mellitus.
	
Measured 180 days prior to drug initiation in any diagnosis position in inpatient or outpatient care setting:
 
DM type 1-At least 1 inpatient or outpatient ICD-9 Dx code of 250.x1 or 250.x3 or ICD-10 Dx code of E10.x in the 12 months prior to drug initiation. 6-months prior
	

2) Treatment (≥ 7 consecutive days) with GLP-1 receptor agonists, other DPP-4 inhibitors or SGLT-2 inhibitors prior to informed consent. Note: This also includes clinical trials where these antidiabetic drugs have been provided to the patient.
	
Measured 180 days prior to drug initiation as a dispensing for one of the following:
 
Treatment (≥ 7 days) with GLP-1 receptor agonists (lixisenatide, dulaglutide, albiglutide, tiraglutide, exenatide), other DPP-4 inhibitors (alogliptin, sitagliptin, saxagliptin) or SGLT-2 inhibitors (canagliflozin, dapagliflozin, empagliflozin) prior to CED
	

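### The as-treated rule lets sulfonylurea patients who add, or start on day 0, a DPP-4 inhibitor other than linagliptin stay in the placebo-proxy arm

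*Combined protocol and SAP*

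**What the plan says.** Section 5.1 uses the "2nd generation sulfonylurea (SU) antidiabetic class as a proxy for placebo". Section 6.1 defines the other arm narrowly: "The study exposure of interest is initiation of linagliptin". The antidiabetic class sheet in Appendix A lists four DPP-4 inhibitors: alogliptin, linagliptin, saxagliptin and sitagliptin.

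The as-treated analysis is primary because it targets the hazard on treatment (Section 6.3.2). It censors at "The date of augmentation or switching from an exposure to a comparator or any other agent in the comparator class and vice versa", and then states that "An added treatment that is not part of the exposure or comparator group does not fulfill this criterion", with added insulin as the example. It also censors when the index drug is discontinued, 30 days after the last supply ends. Section 5.1 gives the general position that "patients are allowed to take other antidiabetic medications during study follow-up".

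Before entry the plan is stricter. Exclusion 2 in Appendix A removes patients with at least 7 days of a GLP-1 receptor agonist, another DPP-4 inhibitor or an SGLT-2 inhibitor. It is "Measured 180 days prior to drug initiation as a dispensing for one of the following", and its text ends at use before the cohort entry date.

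**The concern.** The plan treats other DPP-4 inhibitors as disqualifying before entry and ignores them afterwards. An SU patient who adds one and keeps refilling the SU goes on contributing person-time and events to the arm that stands in for placebo, while taking a drug of the exposure's own class. The same holds from day 0 for someone who starts an SU and sitagliptin together: Exclusion 2 looks backwards only, and the flowchart step for patients qualifying in more than one exposure category concerns the two study groups.

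If the class shares an effect on MACE, this makes the arms more alike. In a non-inferiority comparison against 1.3, a harmful effect would then be easier to miss. Nothing planned would reveal it. The ITT analysis drops switching and augmentation censoring altogether, the secondary analysis in Section 13.2 changes only the propensity-score adjustment, and neither Table 1 nor the censoring table has a row for other DPP-4 inhibitors.

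**Working it through.** **Does the executed analysis match the text?** The reasons-for-censoring table in Section 9 is exhaustive:

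- Referent: 929 + 746 + 29,602 + 9,825 + 4,583 + 5,230 = 50,915.
- Exposure: 775 + 4,006 + 29,190 + 8,343 + 4,607 + 3,994 = 50,915.

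The rows that can reflect a drug change are "Start of an additional exposure", end of index exposure, and switch to other SUs (combined with nursing home admission). None is for another DPP-4 inhibitor.

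**Is the day-0 gap plausible?** Exclusion 2 also bars SGLT-2 inhibitors. In the matched part of Table 1, past SGLT2i use is 1 patient per arm. Concomitant initiation or current use is 51 + 62 + 22 = 135 referent patients (0.27%) and 267 + 559 + 412 = 1,238 exposed patients (2.4%). Patients taking an Exclusion 2 class at entry therefore reach the matched cohort. No corresponding row exists for DPP-4 inhibitors.

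**The plan's own figure.** Pooled inputs from Section 10 are 50,915 per arm, 25.91 per 1,000, margin 1.3, assumed HR 1 and two-sided alpha 0.05.

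- Events = 2 × 50,915 × 0.02591 = 2,638.4.
- Power = Φ(√(2,638.4/4) × ln 1.3 − 1.96) = Φ(25.68 × 0.2624 − 1.96) = 0.9999991, as stated.

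**Size of the dilution.** Let f be the share of SU person-time on another DPP-4 inhibitor. The documents do not give f, so it is varied. Assume these drugs have linagliptin's effect.

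- Observed HR = HR / (1 − f + f × HR), which at HR 1.3 is 1.3 / (1 + 0.3f).
- False non-inferiority rate at true HR 1.3 = Φ(√(2,638.4/4) × ln(1.3 / observed HR) − 1.96).

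| f (assumed) | Observed HR | False non-inferiority rate |
|---|---|---|
| 0 | 1.300 | 2.5% |
| 2% | 1.292 | 3.5% |
| 5% | 1.281 | 5.7% |
| 10% | 1.262 | 11.5% |

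For f = 10%: ln(1.03) × 25.68 = 0.759, and Φ(0.759 − 1.96) = 0.115.

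The result depends on the event count. With Optum's 294 events alone, f = 10% gives 4.4%. The pooled risk of 25.91 is the unweighted mean of the three database risks; summing the database events instead gives 294 + 326 + 2,830 = 3,450, and f = 10% then gives 13.7%.

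**Away from the margin.** At a true HR of 1.0 the observed HR is 1.0 for any f. At the trial's 1.02, even f = 20% gives 1.02 / 1.004 = 1.016, a shift of about 0.004.

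**The case against.** Much of the case on the other side stands.

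- **Switchers leave.** A reader might infer that every SU patient who starts another DPP-4 inhibitor keeps counting as placebo. A patient who replaces the SU is censored through discontinuation plus 30 days. End of index exposure accounts for 58.14% of referent patients, and median referent follow-up is only 122 to 148 days. The gap is limited to add-on and day-0 co-initiation.
- **The pull toward 1 is conditional.** A reader might infer that the rule biases the HR toward 1 as a matter of course. That needs a shared class effect, which the documents do not state, and a true HR away from 1. With a true HR below 1, the same dilution would move the estimate up, toward the margin.
- **The crossover counts are not evidence of contamination.** It is tempting to cite 4,006 (7.87%) exposed against 746 (1.47%) referent patients censored at crossover. These count starts of the other study drug. Unmatched SU initiators outnumber linagliptin initiators 594,152 to 51,041, about 11.6 to 1, so unequal crossover is expected under any rule.
- **The share f has no anchor.** Exclusion 2 removed 4.9% to 6.6% of patients by database (23,347/474,186; 7,712/144,634; 9,388/143,318). That pools three drug classes, both future arms and any qualifying use in 180 days. It is not concurrent DPP-4 inhibitor person-time in the SU arm, and nothing supports a share as high as 20%.
- **Add-on therapy is allowed by design**, as in the trial, and Exclusion 2 copies a trial entry criterion.

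The last point does not settle the matter. General permission for other antidiabetic drugs is not a reason to leave same-class use inside the placebo proxy in an analysis meant to measure the on-treatment contrast. Nor does reading the phrase about the reverse direction in the switching rule as class-wide on the exposure side help: exposure is linagliptin alone, and no row of the censoring table reflects such a reading.

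**Conclusion.** The gap holds, for add-on and day-0 co-initiation only. It conflicts with the plan's baseline exclusion, its use of the SU arm as placebo proxy, and the aim of its primary analysis. The error would be anti-conservative if linagliptin were harmful and the class shared that effect: roughly 3.5% to 11.5% false non-inferiority instead of 2.5%, for an assumed 2% to 10% of SU person-time at 2,638 events and a true HR of 1.3. The actual share is unknown, and at the planning HR of 1.0 or the trial's 1.02 the effect is nil or negligible. Severity is moderate. A reader might infer that the non-inferiority conclusion is already compromised; the documents do not support that, because they give neither the share nor a class effect.

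**What to change.** - In Section 6.3.2, censor as-treated follow-up in **both** arms at the first dispensing of any non-index DPP-4 inhibitor on the Appendix A class sheet.
- Extend the other-DPP-4-inhibitor part of Exclusion 2 to include the cohort entry date, in both arms.
- Add a row by arm for other DPP-4 inhibitor starts to the reasons-for-censoring table.
- Keep the current rule as a prespecified sensitivity analysis.

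The drug list already exists in Appendix A, and Section 13 carries no conduct date, so on the face of the document the change can precede the comparative results. The entry change means repeating the match and the balance and power checks in Sections 9 and 10.

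The costs are slightly less person-time and some extra censoring at treatment intensification, which may be informative; this is why the current rule should stay as a sensitivity analysis. Power is barely touched in the pooled analysis: losing 20% of referent events leaves 2,638.4 × 0.9 = 2,374.6 events and power above 0.999. On the same assumption Optum falls from 0.614 to 0.569 and MarketScan from 0.659 to 0.613.

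### Did printing deaths by arm at the dummy-outcome stage (929 vs 775 of 50,915) undo the plan's outcome-blind design?

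*Combined protocol and SAP*

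**What the plan says.** Section 7 (Initial Feasibility Analysis) is strict about what may be seen: "No measures of association will be computed nor will incidence rates stratified by treatment group". It asks for censoring only in aggregate: "Report reasons for censoring in the overall study population".

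Section 8 (Initial Power Assessment) introduces the dummy outcome, a 90-day enrollment gap, and gives its purpose: "This outcome is used to ensure that no information on the comparative risks of the outcomes of interest are available at this stage". The stop-point that closes Section 8 nevertheless lists what the investigators and the FDA will evaluate, including "reasons for censoring by treatment group, as well as overall rates of outcomes and study power". The Section 10 stop-point uses the same words.

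Section 9 (Balance Assessment after PS matching) reuses the device: "Again, using the dummy outcome of a 90-day gap in database enrollment, complete a 1:1 PS-matched analysis". It then instructs: "Report reasons for censoring by treatment group". The table has a Death row by arm. The primary-outcome risk is reported for both arms combined.

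Under Section 11, study team and advisory board members "should at this stage provide their level of confidence for the success of the RWD study". The timing is fixed: "Deadline for voting on study confidence and listing concerns: 12/20/19".

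Section 13.1 estimates each hazard ratio in the same matched cohort. Section 6.3.2 makes a measured death a censoring event without naming its source. Appendix A defines mortality from the vital status file in Medicare and from discharge status codes in the two commercial databases.

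**The concern.** A dummy outcome cannot mask an outcome that is itself a reason for censoring. Mortality is a secondary outcome and, as implemented, the death component of the primary composite. The dummy outcome had no events in either arm, so it cut no follow-up short. If the Death row uses the Appendix A definition, and ties are set aside, 929 and 775 are essentially the as-treated mortality counts that the Section 14.1 results table was meant to show later.

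The timing adds to the worry. The table was run on 18 November 2019 (Medicare on 30 November). The investigator review is dated 9 December, the FDA review 20 December, and the confidence vote closed on 20 December. If the assurance in Section 8 carries over to Section 9, go/no-go decisions and predictions of success were made with by-arm mortality in view, beside a statement that no comparative information existed. At stake is the credibility of the claim that design choices were settled without sight of results.

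**Working it through.** **1. Reproduce the table.** Inputs are the Section 9 censoring rows.

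- Referent: 929 + 746 + 29,602 + 9,825 + 4,583 + 5,230 = 50,915.
- Exposure: 775 + 4,006 + 29,190 + 8,343 + 4,607 + 3,994 = 50,915.
- Deaths: 929/50,915 = 1.82%; 775/50,915 = 1.52%; 1,704/101,830 = 1.67%.

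All match the printed values. Each patient has one reason, so the table covers the whole matched cohort.

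**2. What a reader can derive from it.** With equal arms, the risk ratio is 775/929 = 0.834. SE(log) = sqrt(1/775 + 1/929 - 2/50,915) = 0.048, giving a 95% CI of 0.759 to 0.917. The difference is 3.0 per 1,000.

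**3. Whether that is an effect estimate.** It is not, because follow-up differs by arm and person-time is not given. Let k be exposed person-time divided by referent person-time. The rate ratio is 0.834/k, with SE(log) = sqrt(1/775 + 1/929) = 0.0487.

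| k (assumed) | Rate ratio | 95% CI |
|---|---|---|
| 1.00 | 0.83 | 0.76-0.92 |
| 0.95 | 0.88 | 0.80-0.97 |
| 0.90 | 0.93 | 0.84-1.02 |
| 0.86 | 0.97 | 0.88-1.07 |
| 0.834 | 1.00 | 0.91-1.10 |

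The interval includes 1 once k is about 0.92 or lower. Section 9 prints median follow-up, exposure versus referent, of 118 vs 122 days in Optum (ratio 0.97) and 127 vs 148 in Medicare (0.86). The upper quartiles give 269/304 = 0.88 and 303/344 = 0.88. Medicare supplies 33,319/50,915 = 65% of each arm. The MarketScan by-arm entries repeat Medicare's, so they add no independent information. Medians and quartiles are not person-time, but a k below 0.92 is plausible.

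**4. How much of the primary outcome this could be.** Against the printed pooled expectation in Section 10, 1,704/2,638.4 = 65%. Against the sum of the three database expectations (293.9 + 326.0 + 2,830.1 = 3,450.0), it is 49%. Both are ceilings under the Appendix A definition, apart from deaths that ties placed in other rows: a death after a non-fatal event is not a first event.

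**5. What was planned and what was withheld.** Read together, the Section 8 and Section 10 stop-points draw a consistent line: censoring by arm, outcome rates overall. The Section 9 table keeps to it. By-arm myocardial infarction, stroke and 3-point MACE do not appear. No change to cohort, propensity score, censoring or outcome definitions is identified after the table was produced.

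**6. What hiding the row would gain.** In a rerun, death could be merged with end of enrollment: 929 + 4,583 = 5,512 (10.83%) vs 775 + 4,607 = 5,382 (10.57%). That would hide differential censoring by death, and the plan schedules no rerun. The existing table shows why censoring by arm deserves review before sign-off: starting the other study drug censored 7.87% of linagliptin patients against 1.47% of referents.

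**The case for a change.** The strongest opposing case is that the plan gives no other purpose for the dummy outcome in Section 9, and that opening with a word of repetition imports the Section 8 assurance. Mortality by arm is comparative outcome information whether or not it is adjusted for person-time. A disclosure sentence, a definition, a label on the mortality result and a change log would cost almost nothing, and the date fields for registration and comparative analyses are still blank.

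Part of this stands. The Section 8 sentence is broader than what was delivered, and it sits in tension with the stop-point in its own section. The Death row is probably the Appendix A variable, but no passage says so.

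The rest is weaker. The assurance is written for the initial power assessment and limited to that stage. No passage claims that the December 2019 sign-offs or the vote were blind to mortality. The table, its run dates, the review dates and the instruction to evaluate it are all printed in the document to be registered, so the facts are already open to any reader. The vote is a confidential rating of confidence, and nothing ties it to the analysis specification. A label for results that are not outcome-blind would bring in a convention that Sections 13 and 14 do not use.

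**Conclusion.** The observation is accurate, but it does not call for a change. By-arm deaths of 929 and 775 were visible before the comparative analyses, as a foreseeable product of a censoring review that the plan announced at both stop-points. The crude ratio of 0.83 (0.76-0.92) should not be read as a mortality effect; with the follow-up printed in the same section, the rate ratio could be near 1. The main comparative results stayed hidden by arm, and no design decision is shown to have moved.

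The remaining gap is one of wording: an assurance phrased too broadly and a row whose definition an analyst would naturally take from Appendix A. A clarifying sentence would do no harm, but it would alter no estimate, test or conclusion. Merging the row would give up a useful check for no gain.

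This rests on three points: the Death row is taken to follow Appendix A; k near 0.86 is an inference from the Medicare medians, not a reported value; and the documents show no change to cohort, propensity score, censoring or outcome definitions after November 2019.
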